### 6.5.3 Instructions for dose modifications or interruption during a cycle.

Table 2: Dose Modifications	
NCI CTC Toxicity Grade (unless otherwise noted)	Dose Modification Instructions
If baseline ANC ≥ 1000/ mm^3: Grade 3 neutropenia associated with fever (temperature ≥ 38.5° C) or Grade 4 neutropenia	
 
Hold (interrupt) lenalidomide dose.
 
Follow CBC weekly.
 
If neutropenia has resolved to ≤ grade 2 prior to Day 21, restart lenalidomide at next lower dose level and continue through the scheduled end of the cycle. Otherwise, omit for remainder of cycle and reduce the dose of lenalidomide by 1 dose level at the start of the next cycle. Omitted doses are not made up. If neutropenia is the only toxicity for which a dose reduction is required, G-CSF may be used and the lenalidomide dose maintained
 

If baseline ANC ≤ 1000/ mm^3: Grade 3 neutropenia associated with fever (temperature ≥ 38.5° C) or ANC < 50% of baseline	
 
Hold (interrupt) lenalidomide dose.
 
Follow CBC weekly.
 
If ANC has recovered to ≥50% of baseline and fever has resolved prior to Day 21, restart lenalidomide at next lower dose level and continue through the scheduled end of the cycle. Otherwise, omit for remainder of cycle and reduce the dose of lenalidomide by 1 dose level at the start of the next cycle. Omitted doses are not made up. If neutropenia is the only toxicity for which a dose reduction is required, G-CSF may be used and the lenalidomide dose maintained
 

If baseline platelet count ≥ 50,000/mm^3: Thrombocytopenia ≥Grade 3 (platelet count < 50,000/mm^3)	
 
Hold (interrupt) lenalidomide dose.
 
Follow CBC weekly.
 
If thrombocytopenia has recovered to ≤ grade 2 prior to Day 21, restart lenalidomide at next lower dose level and continue through the scheduled end of the cycle. Otherwise, omit for remainder of cycle and reduce the dose of lenalidomide by 1 dose level at the start of the next cycle. Omitted doses are not made up.
 

If baseline platelet count < 50,000/mm^3: Platelet count < 50% of baseline	
 
Hold (interrupt) lenalidomide dose.
 
Follow CBC weekly.
 
If platelet count resolves to ≥50% of baseline prior to Day 21, restart lenalidomide at next lower dose level and continue through the scheduled end of the cycle. Otherwise, omit for remainder of cycle and reduce the dose of lenalidomide by 1 dose level at the start of the next cycle. Omitted doses are not made up.
 

Table 2: Dose Modifications	
NCI CTC Toxicity Grade (unless otherwise noted)	Dose Modification Instructions
Non-blistering rash	
 
• If Grade 3, hold (interrupt) lenalidomide dose. Follow weekly.
 
• If the toxicity resolves to ≤ grade 1 prior to Day 21, restart lenalidomide at next lower dose level and continue through the scheduled end of the cycle. Otherwise, omit for remainder of cycle and reduce the dose of lenalidomide by 1 dose level at the start of the next cycle. Omitted doses are not made up.
 

Grade 4	
 
• If Grade 4, discontinue lenalidomide. Remove patient from study.
 

Desquamating (blistering) rash- any Grade	
 
• Discontinue lenalidomide. Remove patient from study.
 

Neuropathy	
 
• If Grade 3, hold (interrupt) lenalidomide dose. Follow at least weekly.
 
• If the toxicity resolves to ≤ grade 1 prior to Day 21, restart lenalidomide at next lower dose level and continue through the scheduled end of the cycle. Otherwise, omit for remainder of cycle and reduce the dose of lenalidomide by 1 dose level at the start of the next cycle. Omitted doses are not made up.
 

Grade 4	
 
• If Grade 4, discontinue lenalidomide. Remove patient from study.
 

Venous thrombosis/embolism ≥ Grade 3	
 
• Hold (interrupt) lenalidomide and start anticoagulation; restart lenalidomide at investigator's discretion (maintain dose level).
 
• Omit lenalidomide for remainder of cycle. See Anticoagulation Consideration (Section 6.6.1.2)
 

Hyperthyroidism or hypothyroidism	
 
• Omit lenalidomide for remainder of cycle, evaluate etiology, and initiate appropriate therapy.
 
• See Instructions for Initiation of a New Cycle and reduce the dose of lenalidomide by 1 dose level.
 

other non-hematologic toxicity ≥ Grade 3	
 
• Hold (interrupt) lenalidomide dose. Follow at least weekly.
 
• If the toxicity resolves to ≤ grade 2 prior to Day 21, restart lenalidomide and continue through the scheduled end of the cycle. Otherwise, omit for remainder of cycle. Omitted doses are not made up. For toxicity attributed to lenalidomide, reduce the lenalidomide dose by 1 dose level when restarting lenalidomide.
 

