#### **6.6.2 Prohibited concomitant therapy**

G-CSF is permitted for neutropenic fever and/or when clinically indicated.

Concomitant use of sargramostim (GM-CSF), other anti-cancer therapies, including radiation, thalidomide, or other investigational agents is not permitted while subjects are receiving study drug during the treatment phase of the study.

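### Table 2 lets patients with baseline ANC of 1000 or more restart lenalidomide mid-cycle on the count alone, although the hold may have been for febrile neutropenia

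*Combined protocol and SAP*

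**What the plan says.** Section 6.5.3, Table 2, has two rows for neutropenia, split by baseline ANC. Each lists Grade 3 neutropenia with fever (at least 38.5 °C) among its reasons to hold lenalidomide. The high-baseline row adds Grade 4 neutropenia, and the low-baseline row adds a fall below half of baseline.

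The restart conditions differ:

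- High baseline: "If neutropenia has resolved to ≤ grade 2 prior to Day 21, restart lenalidomide at next lower dose level".
- Low baseline: "If ANC has recovered to ≥50% of baseline and fever has resolved prior to Day 21, restart lenalidomide at next lower dose level".

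In both rows, if the condition is not met in time, the drug is omitted for the rest of the cycle. Both rows also contain this option: "If neutropenia is the only toxicity for which a dose reduction is required, G-CSF may be used and the lenalidomide dose maintained". Section 6.6.2 adds that "G-CSF is permitted for neutropenic fever and/or when clinically indicated".

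The rows are introduced by "If baseline ANC ≥ 1000/ mm" and "If baseline ANC ≤ 1000/ mm", so a baseline of exactly 1000 belongs to both.

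**The concern.** Fever is half of the shared trigger, but only one row requires it to have gone before dosing resumes mid-cycle. A clinician who follows the high-baseline row exactly may restart the drug in a patient who is still febrile. The only follow-up that row orders is a weekly blood count, so it does not prompt a check of the fever either.

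A recovered count is not a reliable sign that the fever has resolved. G-CSF is allowed for neutropenic fever, so the count can rise first.

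What is at stake is patient safety, not the primary objective or the sample size. The situation is plausible here: Section 6.1.1.3 reports neutropenia and thrombocytopenia in most patients of the phase I/II experience, and Section 4.9 lists infections, sepsis and pneumonia among the most frequently reported events. Entry requires an ANC above only 250/µL (Section 6.2.1), so both baseline groups can enrol. Some visits may be done by local oncologists (Section 2 footnotes), who will depend on the table's wording.

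**Working it through.** The plan states no figure to reproduce. The check compares rules, then follows one illustrative patient through each ANC row.

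**1. Hold trigger against restart condition.** Seven rules in Table 2 tie a mid-cycle restart to a recovery criterion.

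| Rule | Reason for hold | Needed to restart before Day 21 |
|---|---|---|
| ANC, high baseline | Grade 3 with fever, or Grade 4 | Neutropenia ≤ grade 2; **fever not addressed** |
| ANC, low baseline | Grade 3 with fever, or ANC < 50% of baseline | ANC ≥ 50% of baseline and fever gone |
| Platelets, high baseline | ≥ Grade 3 | ≤ grade 2 |
| Platelets, low baseline | < 50% of baseline | ≥ 50% of baseline |
| Non-blistering rash | Grade 3 | ≤ grade 1 |
| Neuropathy | Grade 3 | ≤ grade 1 |
| Other non-hematologic | ≥ Grade 3 | ≤ grade 2 |

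The venous thrombosis row (investigator's discretion) and the thyroid row (omit for the rest of the cycle) set no recovery criterion for a mid-cycle restart and are not counted. In 1 of the 7 rules, the high-baseline ANC rule, a sign named in the trigger is not addressed at restart.

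**2. Search for a rule elsewhere that fills the gap.**

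- Section 6.5.2 governs Day 1 of a new cycle and does not name fever.
- The last row of Table 2 ("If the toxicity resolves to ≤ grade 2 prior to Day 21, restart lenalidomide and continue through the scheduled end of the cycle") applies to toxicity of Grade 3 or higher and does not name fever.
- Sections 6.1.1 and 6.7 give general discretion to stop treatment; they set no restart condition.
- Section 6.6.2 permits G-CSF and says nothing on restart.

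**3. Worked case.** Assumed patient: 10 mg starting dose; held on Day 8 for Grade 3 neutropenia with 39.0 °C; on Day 15 the count meets the row's criterion but the temperature is 38.8 °C. From Table 1, the next dose level is 5 mg daily.

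- Baseline 1200, restart on Day 15: 28 − 15 + 1 = 14 dosing days; 14 × 5 mg = 70 mg. If the G-CSF option keeps the dose at 10 mg: 14 × 10 mg = 140 mg.
- Baseline 1200, restart on Day 20, the last day before Day 21: 28 − 20 + 1 = 9 dosing days; 9 × 5 mg = 45 mg, or 9 × 10 mg = 90 mg.
- Baseline 950: the hold continues while the fever lasts. If it has not resolved before Day 21, the rest of the cycle is omitted: 0 mg.

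The contrast does not depend on the grade cut-offs, which the protocol does not print. Whatever the Grade 2 limit is, the high-baseline row permits restart once it is reached, at any temperature.

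**4. The boundary.** A baseline of exactly 1000 satisfies both ANC rows, which disagree on fever. The platelet rows avoid this: one begins "If baseline platelet count ≥ 50,000/mm" and the other takes baselines strictly below 50,000.

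**The case against.** The strongest counter-argument is structural. In the high-baseline row the febrile trigger needs fever and Grade 3 neutropenia together, so once the count is at grade 2 or better the trigger is no longer met. In the low-baseline row, a patient held for febrile Grade 3 neutropenia may already be at half of baseline on the day of the hold; without a fever clause that hold could lapse at once. The asymmetry may therefore be deliberate. This explains why the low-baseline row needs the clause. It does not make restarting during the fever sound in the other row, and the protocol offers no such reasoning.

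Other points deserve weight:

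- The 1-in-7 count can be disputed, because the low-baseline row holds on a grade but restarts on a percentage of baseline. That row does, however, address both the count and the fever. The different restart counts are not questioned here.
- The low-baseline protection applies only mid-cycle; Section 6.5.2 would not stop a new cycle for a persisting low-grade fever. The concern is limited to mid-cycle restarts accordingly.
- Safeguards exist: restart is one dose level lower by default, and investigators may withhold or stop the drug. Many would wait. They reduce the risk but do not replace the condition.
- The 90 and 140 mg figures need the G-CSF option, and whether an ongoing febrile illness still leaves neutropenia as the only toxicity requiring reduction is open to interpretation.
- The worked case shows exposure, not harm.

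**Conclusion.** The concern holds. The same febrile trigger appears in both ANC rows, and only the low-baseline row requires the fever to resolve before a mid-cycle restart. For the illustrative patient, the difference over the rest of the cycle is 45 to 70 mg at the reduced dose, or 90 to 140 mg if the G-CSF option applies, against 0 mg where the fever lasts to Day 21 in a low-baseline patient. These figures rest on the assumed hold and recovery days and the 10 mg starting dose. How many of the 56 patients would be affected cannot be derived from the documents.

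This is a safety inconsistency that should be corrected; it does not bear on the trial's sample size or primary analysis. The overlap at a baseline of exactly 1000 is a minor editorial slip.

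**What to change.** In the high-baseline ANC row of Table 2, insert *and fever has resolved* after the grade 2 criterion and before the Day 21 limit. A hold for afebrile Grade 4 neutropenia is unaffected. In the heading of the low-baseline row, change ≤ 1000 to < 1000 so that each baseline value falls under one row. Leave the restart counts as they are.

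The cost is an amendment of a few words and one symbol, with no added procedures. A few febrile high-baseline patients may stay on hold somewhat longer.

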- Clinical toxicity has been infrequent with administration of REVCLIMID® (see section 4.9). Cases of neutropenia and thrombocytopenia have been reported in the phase I/II experience in the majority of patients and appear to be dose and/or duration dependent. MDS patients with existing neutropenia and/or thrombocytopenia should be monitored closely during treatment for potential exacerbation that may merit a treatment hiatus and dose reduction as described below.

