#### **Inclusion criteria**

1. Understand and voluntarily sign an informed consent form.

2. Age  $\geq$  21 years at the time of signing the informed consent form.
  3. Able to adhere to the study visit schedule and other protocol requirements.
  4. A confirmed diagnosis (using standard FAB criteria) of a myelodysplastic syndrome with low/Int-1 risk and with a non-del(5q) karyotype must be established.
  5. Patients must have transfusion dependence (at least 2 units within 8 weeks prior to starting therapy).
  6. All transfusion dependent **non**-del(5q) low/Int-1 risk patients will be eligible for treatment with Revlimid®
  7. Newly diagnosed as well as previously treated patients will be eligible
  8. Patients with primary de novo or secondary MDS will be eligible
  9. All previous cancer therapy, including radiation, hormonal therapy and surgery, must have been discontinued at least 4 weeks prior to treatment in this study.
10. ECOG performance status of 0-2 at study entry (see Appendix II).
11. Laboratory test results within these ranges:
- Absolute neutrophil count  $> 250/\mu\text{L}$
  - Platelet count  $> 30,000/\mu\text{L}$
  - Serum creatinine  $\leq 2.0 \text{ mg/dL}$
  - Total bilirubin  $\leq 1.5 \text{ mg/dL}$
  - AST (SGOT) and ALT (SGPT)  $\leq 3 \times \text{ULN}$
  - BUN  $\leq 2 \times \text{ULN}$
12. Disease free of prior malignancies for  $\geq 2$  years with exception of currently treated basal cell, squamous cell carcinoma of the skin, or carcinoma "in situ" of the cervix or breast.
13. All study participants must be registered into the mandatory RevAssist® program, and be willing and able to comply with the requirements of RevAssist®.

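### In Table 2's low-baseline ANC row, fever triggers a hold only at Grade 3, so a febrile Grade 4 patient with ANC at or above half of baseline meets neither trigger

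*Combined protocol and SAP*

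**What the plan says.** Section 6.5 directs that dosing be modified according to Table 2 in Section 6.5.3. The table has two ANC rows.

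- **Baseline ANC 1000 or more.** The triggers are "Grade 3 neutropenia associated with fever (temperature ≥ 38.5° C) or Grade 4 neutropenia". Restart within the cycle depends on neutropenia improving to Grade 2 or better.
- **Low baseline.** This row opens with "If baseline ANC ≤ 1000/ mm"³. Its triggers are "Grade 3 neutropenia associated with fever (temperature ≥ 38.5° C) or ANC" below "50% of baseline". Its restart condition reads "If ANC has recovered to ≥50% of baseline and fever has resolved prior to Day 21".

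Elsewhere the same table marks a grade or anything worse with a ≥ sign. An example is the platelet row, "Thrombocytopenia ≥Grade 3 (platelet count" below 50,000). The thrombosis and other non-hematologic rows do the same. The non-blistering rash and neuropathy rows give Grade 3 and Grade 4 different instructions.

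Inclusion criterion 11 (Section 6.2.1) admits patients with an "Absolute neutrophil count" above 250/µL. Section 6.1.1.3 adds: "MDS patients with existing neutropenia and/or thrombocytopenia should be monitored closely during treatment for potential exacerbation".

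**The concern.** A hold rule for falling counts would be expected to act at least as readily on a worse count as on a better one, unless the protocol explains otherwise. In the low-baseline row it does not always do so. Between half of baseline and the Grade 4 limit, a febrile patient has no trigger. Just above that limit, the same fever is a trigger.

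The row governs patients with pre-existing neutropenia, whom Section 6.1.1.3 singles out for close observation. Section 4.9 lists neutropenia, infections and sepsis among the reported events. Section 2 (footnotes 14 and 15) lets local oncologists perform some visits in Cycles 1 to 3, so the written table may be applied away from the study center. Two sites reading this row could act differently on the same patient.

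**Working it through.** The plan states no figure to reproduce. The check applies the row literally.

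**Inputs**
- Low-baseline row (Section 6.5.3): hold if fever with Grade 3 neutropenia, or if ANC is below half of baseline with or without fever.
- Lowest eligible baseline: just above 250/µL (criterion 11).
- Grading scale: NCI CTC/CTCAE version 3.0 (Section 7.2, Appendix III). Neutrophil limits are not printed. Assumption: Grade 3 is 500 to below 1000 and Grade 4 is below 500. The Grade 4 limit c is also varied to 400 and 300.

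**Rule for a febrile patient with baseline B and count A**

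Hold = (c ≤ A < 1000) or (A < 0.5 × B).

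Neither trigger is met when 0.5 × B ≤ A < c. This range is non-empty only if 0.5 × B < c, that is B < 2c. Counts above the patient's own baseline are left out, because they are improvements.

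**Uncovered febrile Grade 4 counts (/mm³)**

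| Baseline | c = 500 | c = 400 | c = 300 |
|---|---|---|---|
| 900 | 450–499 | none | none |
| 800 | 400–499 | none | none |
| 600 | 300–499 | 300–399 | none |
| 500 | 250–499 | 250–399 | 250–299 |
| 400 | 200–400 | 200–399 | 200–299 |
| 300 | 150–300 | 150–300 | 150–299 |
| 251 | 126–251 | 126–251 | 126–251 |

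The gap closes at baseline 1000 for c = 500 (2 × 500), at 800 for c = 400 and at 600 for c = 300.

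**One patient, baseline 800, fever, c = 500**
- ANC 600 (Grade 3): held.
- ANC 450 (Grade 4; 450/800 = 56%): neither trigger met.
- ANC 390 (Grade 4; 390/800 = 49%): held.

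**Baselines below 500, c = 500.** These patients are already Grade 4 at entry. The fever trigger cannot act unless the count rises to 500 or more.

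**Hold against restart, baseline 400 (half = 200).** A patient held at 180 who recovers to 210 but is still febrile does not meet the restart condition. A febrile patient at 210 who never fell below 200 is not held by this row. The same count and the same fever give two outcomes.

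**Baseline exactly 1000.** Both rows apply. With c = 500 their hold triggers coincide, since Grade 4 and below half of baseline both mean below 500. Their restart rules do not. Grade 2 or better means at least 1000 under the assumed limits, while half of baseline means at least 500, with fever resolved. The two platelet rows avoid this overlap by using ≥ and <.

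**The case against.** A reader might infer that this row leaves every febrile Grade 4 patient on treatment. The documents do not support that, for two reasons.

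- The second trigger holds any count below half of baseline, with or without fever. The gap is confined to Grade 4 counts at or above that level.
- Section 6.1.1 lets the Principal Investigator stop therapy for a serious adverse event, and Section 6.7 allows stopping on the investigator's judgment. Table 2 also requires a hold for other non-hematologic toxicity of Grade 3 or worse, which could capture a febrile event depending on how it is classified. These routes may apply, but the first two are discretionary discontinuations and the third depends on coding. None is a neutropenia rule that requires a hold.

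It can also be argued that Grade 3 with fever was meant as a floor. The separate naming of Grade 4 in the higher-baseline row does not settle this, because there Grade 4 triggers a hold without fever and has to be named anyway. The fever clause in the restart rule suggests that fever was meant to matter. Against that, the table uses ≥ where it means a grade or worse, and separates Grades 3 and 4 for rash and neuropathy. Nor is the floor reading a harmless correction. With a Grade 4 limit of 500, it would hold a patient with baseline below 500 for a qualifying fever at an unchanged count, the opposite action to the literal reading.

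Finally, omitting a stand-alone Grade 4 trigger looks deliberate, since some eligible patients may start at Grade 4. A baseline-relative trigger also matches the low-baseline platelet row and the new-cycle rule in Section 6.5.2. That argument stands. It explains why Grade 4 alone is not a trigger, but not why fever counts at Grade 3 and not at Grade 4.

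**Conclusion.** The point holds as a confined inconsistency in a safety rule. On the literal wording, a febrile Grade 4 patient with ANC at or above half of baseline meets neither trigger, although a febrile Grade 3 patient is held. The row's restart condition takes account of fever in a way its hold trigger does not.

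The size depends on an assumption. With Grade 4 below 500, the gap affects baselines below 1000 and, for baselines under 500, covers every count from half of baseline up to baseline. With limits of 400 or 300 it is restricted to baselines below 800 or below 600. Baseline is treated as one fixed value per patient. The documents give no basis for estimating how many patients would fall in the band.

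A reader might also infer that dose-hold data in this subgroup would cease to reflect toxicity. The documents do not support this: dose holds are not an endpoint in Section 5.2, and toxicity is graded separately (Sections 7.2 and 11.5).

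The overlap at a baseline of exactly 1000 is minor, but it is real because the restart rules differ.

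**What to change.** The sponsor and investigator should amend the low-baseline ANC row of Table 2 so that:

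1. its hold trigger is reconciled with its own restart condition, with the row for baseline 1000 or more, and with the ≥ notation used elsewhere in the table;
2. it states whether febrile Grade 4 neutropenia is covered by this row;
3. a baseline of exactly 1000 belongs to one row only.

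Which counts and temperatures should lead to a hold is a clinical decision for them. No threshold is proposed here.

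The cost is an amendment to the ANC rows of one table. The downside is possibly a few more or fewer dose holds among patients with low baseline ANC, depending on which reading is confirmed.

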#### 6.5.4 Treatment compliance

Research center personnel will review the dosing instructions with subjects. Subjects will be asked to maintain a diary to record the drug administration. Subjects will be asked to bring any unused study drug and empty study drug containers to the research center at their next visit. Research personnel will count and record the number of used and unused study drug capsules at each visit and reconcile with the patient diary.

Any unused Revlimid® (lenalidomide) should be returned to the patient for disposition in accordance with the RevAssist® program.

## **6.6 Concomitant therapy**

### **6.6.1 Recommended concomitant therapy**

Subjects should receive full supportive care, including transfusions of blood and blood products, antibiotics, and antiemetics when appropriate.

#### **6.6.1.2 Anticoagulation Consideration**

Lenalidomide increases the risk of thrombotic events in patients who are at high risk or with a history a thrombosis, in particular when combined with other drugs known to cause thrombosis. When lenalidomide is combined with other agents such as steroids (e.g. dexamethasone, prednisone), anthracyclines (Doxil, Adriamycin) and erythropoietin the risk of thrombosis is increased.

Consideration should be given to the requirement or optional use of aspirin (81 or 325 mg) or some other form of prophylaxis as deemed appropriate. Low molecular weight heparin may be utilized in patients that are intolerant to ASA. Coumadin should be used with caution and close monitoring of INR.

